- **Adolescent Grouping.** To group adolescents during the GSA-ASPIRE-Network condition (details in Appendix 6), the variable indicating intention to use tobacco will be dichotomized (0=no intention; 1=some intention). At time 1, adolescents who intent to use or are using tobacco will be matched with 2 to 4 adolescents who are closest in distance and do not intent to use tobacco. This ratio is chosen based on previous research showing that 20%-40% of adolescents report some intention to use (average, 33%). If assignment of adolescents to group faces difficulties, we may rely on a continuous measure of intention to use tobacco. Adolescents who indicate intent/use will remain the minority in each group. This design should play a role in preventing at-risk adolescents from influencing their group peers.

The PI along with a statistical analyst and statistician will privately meet in-house at the department in order to make decisions about the intended groupings based on the network data. The study staff will not be present at these meetings. They will be blinded to the basis of the grouping. As a result, they will implement the groupings at the ASPs without knowing the basis of the grouping, thereby insuring that the intended groupings are achieved without disclosing its basis to the participants.

- **Sample Size Considerations for Study 2.** Summary statistics were obtained from the original trial. For H1, given 2 clusters per arm with an average of 25 adolescents who intent to use tobacco in each cluster (n=100) and intra-class correlation (ICC) of 0.3, 80% power is achieved using a two-sided test, with significance  $p<0.05$  to detect a difference in positive social influence in the ASPIRE arm of 1.0 and the GSA-ASPIRE-Network of 2.43 assuming a common standard deviation of 0.8. A difference will be detected

in intention to use tobacco in the ASPIRE arm of 1.3 and GSA-ASPIRE-Network of 0.17 assuming a common standard deviation of 0.5.

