Susceptibility to use tobacco is a clinical and epidemiological screening questionnaire of 3 items that has been shown to be the most potent predictor of actual tobacco initiation among adolescents. The continuous version of this scale is termed “intention to use tobacco”. Sample size and power have been calculated based on the hypothesized difference between groups that render participants in the GSA-ASPIRE-Network group non-susceptible to use tobacco, based on the “intention to use tobacco” scale and previous research.

Sample size calculation is done for H1 and satisfies H2. These power estimates are conservative. We will have more power using mixed-effect models. Sample size was calculated based on 2 clusters per arm, however, we will have more power with the proposed 8 clusters (4 clusters per arm). Considering that about 33% of adolescents generally intent to use tobacco, the required sample size is 300 participants. Considering 40% retention and 50 potential non-eligible, we will recruit 800 participants. In addition to this sample size, we will work to reach a representative Florida sample of adolescents. For the interviews, thematic saturation with adolescents is expected by 60 interviews (20% of the final 300 participants).

- **Quantitative data analysis for Study 2.** To test H1, a linear mixed-effect model (LMM) will be conducted to compare the conditions with respect to intention to use tobacco (continuous outcome variable), in a 2 (condition)  $\times$  4 (time) design. Using a second LMM, the 2 conditions will be compared over time with respect to positive social influence. In both models, intervention effects on outcome trajectories over time will be measured with the condition  $\times$  time interaction term. To test H2, a third LMM will be conducted with positive social influence as a mediator. Each individual will be modeled as a random effect nested within the club, club membership will be modeled as a random effect nested within treatment condition, and treatment will be modeled as a fixed effect. If manipulation checks indicate problems, particularly differences or similarities between arms that are not supposed to occur, we will control for such differences or similarities within our models.

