#### • **Justification for number of participants for Study 1 and study 2**

	Study 1	Study 2	Studies Combined
Participants needed to complete study:	63	300	363
Additional participants enrolled but may discontinue:	30	450	480
Additional participants needed to undergo screening:	7	50	57
Total number of participants:	100	800	900

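### The H1 power figure is calculated for adolescents who intend to use tobacco, but the H1 models carry no such restriction and no analysis population is named, so the stated 80% does not describe the test as written.

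*Combined protocol and SAP*

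**What the plan says.** All of the following is in section 7 of the combined protocol and SAP unless noted.

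- **Power calculation (Sample Size Considerations for Study 2).** H1 power is worked out for 2 clubs per arm "with an average of 25 adolescents who intent to use tobacco in each cluster (n=100"), with an ICC of 0.3 and a two-sided 5% test. The 80% is attached to positive social influence (1.0 versus 2.43, SD 0.8). For intention (1.3 versus 0.17, SD 0.5) the text says a difference will be detected but gives no percentage.
- **Basis of the effect.** The section says the calculation rests on "the hypothesized difference between groups that render participants in the GSA-ASPIRE-Network group non-susceptible to use tobacco".
- **Step from 100 to 300.** "Considering that about 33% of adolescents generally intent to use tobacco", the section puts the requirement at 300 participants.
- **Reassurance.** "These power estimates are conservative. We will have more power using mixed-effect models". It adds that 8 clubs will give more power than the 4 used in the calculation.
- **Hypothesis (section 5, Study 2).** H1 compares adolescents in the two groups and does not mention baseline intention.
- **Eligibility.** Intention to use tobacco is not required.
- **Adolescent Grouping.** In the intervention arm, "adolescents who intent to use or are using tobacco will be matched with 2 to 4 adolescents" who have no such intention, so non-intenders are participants and form the majority of each group. The intending share is given as "20%-40% of adolescents report some intention to use (average, 33"%).
- **Analysis.** The "linear mixed-effect model (LMM) will be conducted to compare the conditions with respect to intention to use tobacco (continuous outcome variable") is a 2 (condition) by 4 (time) model. A second model handles positive social influence. Neither has a restriction, a subgroup term or a named analysis set.

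**The concern.** A power statement is useful only if it refers to the population and contrast that will be tested. Here the calculation counts only intenders and assumes an effect that takes them to non-susceptible. The models, as far as the text goes, take in everyone, and on the plan's own share two thirds of those adolescents start with no intention to lose.

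Three things are at stake. First, the power of the reported result cannot be read from the plan. Second, the remark that the estimates are conservative compares a calculation in one population with a model in another. Third, an intervention that works exactly as planned in intenders could appear in the primary model as about one third of the planned effect. No intender analysis is pre-specified, so recovering the planned contrast afterwards would be post hoc.

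**Working it through.** **1. Reproduce the plan's figure.** Inputs from Sample Size Considerations for Study 2: 2 clubs per arm, 25 intenders per club, ICC 0.3, two-sided 0.05.

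- Design effect = 1 + (25 − 1) × 0.3 = 8.2
- Effective n per arm = (2 × 25) / 8.2 = 6.10
- Degrees of freedom = 2 × 6.10 − 2 = 10.2
- Noncentrality = (difference / SD) × √(6.10 / 2)

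| Outcome, intenders only | Difference | SD | Noncentrality | Power |
|---|---|---|---|---|
| Positive social influence | 2.43 − 1.0 = 1.43 | 0.8 | 3.12 | 80.4% |
| Intention to use tobacco | 1.3 − 0.17 = 1.13 | 0.5 | 3.95 | 94.5% |

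A t-test on the effective sample size thus returns the stated 80% for positive social influence, and 1.43 is the smallest difference (to two decimals) that reaches 80% by this method. The figure belongs to 100 intenders.

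**2. Trace the 300.** 100 / 0.33 = 303, which the plan gives as 300. Recruitment is (800 − 50) × 0.40 = 300. So 300 is the number of completers expected to contain 100 intenders. It was not derived from a test in 300 adolescents.

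**3. Count who enters the model as written.** Non-intenders among completers: 0.67 × 300 = 201. The table of participant numbers adds 450 under "Additional participants enrolled but may discontinue", giving 750 enrolled. If the mixed models use all available data, non-intenders number about 0.67 × 750 = 503.

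**4. Translate the planned effect.** Assumption, not in the documents: intenders respond as planned and non-intenders do not change. The all-participant difference in intention is the share × 1.13:

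- 20% share: 0.20 × 1.13 = 0.23
- 33% share: 0.33 × 1.13 = 0.37
- 40% share: 0.40 × 1.13 = 0.45

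A preventive effect in non-intenders would make these larger.

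**5. Why this cannot be turned into a power figure.** The SD cannot simply be carried over. Suppose 0.5 is the intender SD and non-intenders sit at 0 on the scale (both assumptions). Mixing the two groups adds 0.33 × 0.67 × 1.3² = 0.374 to the variance in the ASPIRE arm and 0.33 × 0.67 × 0.17² = 0.006 in the other arm.

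- Non-intenders constant: arm variances 0.374 + 0.33 × 0.25 = 0.456 and 0.006 + 0.083 = 0.089; SD averaged over arms √0.2725 = 0.52.
- Non-intenders varying with SD 0.5: arm variances 0.374 + 0.25 = 0.624 and 0.006 + 0.25 = 0.256; SD averaged over arms √0.440 = 0.66.

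The plan does not say whether SD 0.5, SD 0.8 and ICC 0.3 describe intenders or the whole sample. The ICC of a mixed sample may differ from that of intenders, and the tested term is a condition by time interaction. For positive social influence there are no non-intender values at all, so not even step 4 can be done without inventing an effect.

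**The case against.** **The target may be intenders.** The plan names no analysis set, so the all-participant reading is inferred from the absence of a restriction together with the general wording of H1. Dividing 100 by 33% is coherent if H1 is meant for intenders, and the mechanism in the Abstract and Background concerns at-risk adolescents. On that reading the power population is right and the analysis section has left out a restriction. This stands as a possible reading. It does not remove the point, since the plan must then state the restriction, but it does mean that both repairs should be offered equally.

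**Power may be adequate.** This also stands. A reader might infer from the drop from 1.13 to 0.37 that the trial is underpowered. The documents do not support that. No effect in non-intenders is an assumption, and lower uptake of intention among them is plausible in a prevention study. Repeated measures with a baseline may recover precision, and the whole-sample SD and ICC are unknown. A reader might equally infer that the claim of conservatism is false. Within intenders, its point about the number of clubs is sound: the method of step 1 with 100 intenders in 8 clubs gives about 98% for positive social influence and 99.9% for intention. The claim simply has not been shown for a model in all participants.

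**The 80% belongs to the other outcome.** It is written for positive social influence, while the quoted model is for intention. Both are H1 outcomes, both calculations sit in the same intender sample, and both models are unrestricted, so the mismatch applies to each.

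**Conclusion.** The mismatch is established from the text and the plan's own arithmetic. The 80% is the power for positive social influence in 100 intenders, and 300 is the number of adolescents expected to contain them. The H1 models as written would add about 200 non-intenders among the completers. The 80% and the statement that it is conservative therefore do not describe that test.

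The size can be given only for the difference in intention: about 0.37 (0.23 to 0.45) against the planned 1.13, assuming the planned response in intenders and no change in non-intenders. No shortfall in power is shown, and none should be inferred. The point should be fixed because it concerns the population for the primary outcome and leaves the power of the reported test unstated.

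**What to change.** In Quantitative data analysis for Study 2, name the H1 population. Either choice resolves the point:

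- **(a) Intenders.** Restrict both H1 mixed models to adolescents with intention to use tobacco at time 1. This matches the n=100 calculation. Baseline is completed before clubs are randomised, so the subgroup is fixed before allocation.
- **(b) All participants.** Label the existing 80% as applying to intenders only. Restate power for both H1 outcomes under the planned condition by time model, using a whole-sample difference, an SD that includes the intender and non-intender mixture, and a range of ICCs. Use one stated degrees-of-freedom convention for 8 clubs and for the minimum of 4. Pre-specify the same models in time 1 intenders as a named secondary analysis.

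Under either choice, say which population SD 0.5, SD 0.8 and ICC 0.3 describe. Also say whether current users count as intenders, since the grouping and randomisation sections include users while the n=100 names only those who intend to use.

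The cost is wording under (a), and wording plus one recalculation under (b). No new data, visits or participants are needed. The downside of (b) is that the stated power may become less favourable and one more labelled analysis is run.

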## 7. Research Plan for Study 2:

- **Study Design.** Study 2 will address Specific Aim 2 and will involve a nested, group-randomized controlled design, recruiting adolescents from ASPs, such as the Boys and Girls Clubs in Florida. In a 2 (condition) by 4 (time) design, 4 clubs minimum will be randomly assigned to one of two conditions named “ASPIRE” and “GSA-ASPIRE-Network”. Additional ASPs may be recruited in case sample size is not reached.
- Similar to a “wait-list” group, participants in the “ASPIRE” group will receive the GSAs and Network (GSA-Network) portions of the program about 4 weeks following Survey Assessment 4 (A4), between Assessments 5 and 7, in 5 to 7 sessions (5 regular sessions and up to 2 booster sessions). This will include 4 additional assessment points following Assessment 4. With 4 additional assessment points following Assessment 4, we will get to examine improvement over time following participants' engagement in the social features of the program. Participants in the ASPIRE-only group did not have the opportunity to engage with these social features of the program during the Fall.
- To assess long term success among participants in the “GSA-ASPIRE-Network” group, 2 assessment points will be added to this group (A5 and A8 only).
- Survey assessments A5 through A8 will be the same as the network assessment survey (Appendix 4).

- **Eligibility.** An ASP is eligible if it provides internet connection at its club and houses at least 10 adolescents. Adolescents will be eligible if (1) they are of ages 11-18 years, (2) they are members of ASP, (3) they are English-speaking, and (4) have not participated in an educational program about tobacco in the last year. Adolescents with developmental disability, mental or physical, are not excluded from the study. However, they will only be able to participate if (1) they understand the information presented to them in the consent document, and (2) they believe they are capable to engage in the board game, use the internet, and answer survey questions.
- **Methods for Study 2.** The following section describes the methods being used and step-by-step procedures to conduct the study.

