The parents and adolescents will be given the option to download an electronic copy of the signed online informed consent form for their own records or a copy of the one-page parent permission consent form that they reviewed.

Parents and adolescents may use their computers to sign the e-consent.

If research staff are to work with parents, adolescents, and ASP staff inside the ASP facility, research staff will follow COVID-19 guidelines put in place by the ASP. Research staff will wear masks, use hand sanitizer, and will distance themselves from others by at least 6 feet. If someone at the facility were to test positive for COVID-19, all who were in contact with the positive case will be required to quarantine for 2 weeks.

[figure not shown]
It is expected that 1000 adolescents and their parent/legal guardian will be interested and eligible. Parental permission and child assent forms will be presented online, and in detail by a study staff or the PI.

Both program implementers and ASP staff members will receive adult consents to participate in focus group discussions and interviews.

- **Baseline assessment at Day 1:** In a classroom setting, participating adolescents will be invited to complete the baseline 20-minute psychosocial survey (time 1) and the baseline 20-minute social network survey (time 1).
- **Randomization at Day 1:** Immediately after baseline assessment at Day 1, the participating clubs will be randomly assigned to either ASPIRE or GSA-ASPIRE-Network. Details on each intervention are described in the following sections. After-school programs (ASPs) will be randomized in a single-blinded format to 1 of 2 conditions: the ASPIRE program or the GSA-ASPIRE-Network program. We will use a covariate-constrained approach in randomizing ASPs to minimize between-group differences in club characteristics (e.g., adolescent volume in a cluster, proportion of adolescents with intent to use tobacco or users, age, gender).

- **Orientation at Day 1:** Also, after baseline assessment at Day 1, participants will receive a session of orientation, allowing them to learn how to take part in the program (ASPIRE or GSA-ASPIRE-Network), depending on their assigned condition. The orientation will be in the form of a presentation and some attempts at engaging in the program for the first time.

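### The Study 2 mixed model names no between-club variance in change, so the H1 condition × time test can exceed 5% false positives under the usual degrees of freedom if clubs differ in change

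*Combined protocol and SAP*

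**What the plan says.** All places are in section 7, Research Plan for Study 2.

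- **Unit of randomisation.** Randomization at Day 1 states that "the participating clubs will be randomly assigned to either ASPIRE or GSA-ASPIRE-Network". Study Design adds: "In a 2 (condition) by 4 (time) design, 4 clubs minimum will be randomly assigned to one of two conditions".
- **H1 test.** Quantitative data analysis compares intention to use tobacco (the primary outcome), and in a second model positive social influence, over four times. There, "intervention effects on outcome trajectories over time will be measured with the condition" × time interaction term.
- **Random effects.** The same paragraph gives these: "individual will be modeled as a random effect nested within the club, club membership will be modeled as a random effect nested within treatment". Treatment is fixed. It names no club slope, club × time term, residual covariance, robust variance or degrees-of-freedom method, and no other section does.
- **Clustering in the sample size.** Sample Size Considerations assumes "25 adolescents who intent to use tobacco in each cluster (n=100) and intra-class correlation (ICC) of 0.3", applied to a difference in arm values. It gives no ICC for change. It later says "we will have more power with the proposed 8 clusters (4 clusters per arm").
- **Time coding.** Study Design treats time as a four-level factor, while the analysis paragraph speaks of trajectories. Neither says whether time enters as a line or as four levels.

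**The concern.** A random intercept for club adjusts a comparison of arm levels for clustering. It does not adjust a comparison of change: whatever is constant in a club over the four assessments drops out of every within-person difference. The interaction is then judged against within-person residual error, which is the right yardstick only if clubs share the same trajectory apart from the intervention.

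Identical club trajectories need defending here. Peer influence within clubs is the premise of the trial, sessions are scheduled around each site, sites include both clubs and schools, and delivery may be in person or web-based, by several implementers and two teachers.

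At stake is the only stated test of H1, in both models. If clubs drift differently, standard errors are too small, and a significant interaction could reflect a few clubs' drift and not the intervention.

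**Working it through.** **1. The plan's own figures.** With 25 per cluster and ICC 0.3, the design effect is 1 + 24 × 0.3 = 8.2, so 50 per arm is worth 50/8.2 = 6.1. For positive social influence the difference is 2.43 - 1.0 = 1.43 with SD 0.8, so SE = 0.8 × √(2/6.1) = 0.458 and 1.43/0.458 = 3.12. A two-sided t test on 2 × 6.1 - 2 = 10.2 df has 80.4% power, which matches the stated 80%. Recruitment also reproduces: 100/0.33 = 303, about 300; 300/0.40 + 50 = 800. The 0.3 enters only a comparison of arm values and says nothing about how much clubs differ in change.

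**2. The interaction test under the intercept reading.** Take no intervention effect, balanced complete data, K clubs of m adolescents, within-person residual variance s² and club × time variance t². Define the ICC of change as ρ = t²/(t² + s²); this is an assumption, as the documents give no value. The club and person intercepts cancel. For a linear-time contrast:

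- numerator mean square: s² + c·m·t², with c = 1 if club deviations are independent across assessments, and c = 3 if the same variance lies wholly on a linear club drift;
- denominator: the pooled residual, close to s².

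The test statistic's variance is therefore inflated by about λ = 1 + c·m·ρ/(1-ρ), and the false-positive rate is about P(|Z| > 1.96/√λ). This closed-form test agreed with a fitted mixed model in three of three trial datasets.

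**3. Numbers at ρ = 0.01** (ρ/(1-ρ) = 0.0101). Club sizes: 300 completers over 8 clubs is about 37, and over the 4-club minimum 75. At-risk adolescents (33%) number about 12 per club with 8 clubs, or the plan's 25 with 4.

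| Layout | λ, independent / linear drift | Linear time, from λ | Four-level time (3 df), simulated |
|---|---|---|---|
| 8 clubs of 37 | 1.37 / 2.12 | 9% / 18% | 13% / 13% |
| 4 clubs of 75 | 1.76 / 3.27 | 14% / 28% | 21% / 21% |
| 8 clubs of 12 (at-risk only) | 1.12 / 1.36 | 6% / 9% | 7% / 7% |
| 4 clubs of 25 (at-risk only) | 1.25 / 1.76 | 8% / 14% | 10% / 10% |

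Example, 8 clubs of 37 with independent deviations: λ = 1 + 37 × 0.0101 = 1.374, and 1.96/√1.374 = 1.67, giving 9%. Simulation of the exact sums of squares gave the same linear-time figures. At ρ = 0 every layout gives 5%.

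**4. Does a change of reference distribution repair it?** Put 2(k-1) = 6 df on the intercept-only statistic (8 clubs of 37, linear time). The rate is about 1.5% at ρ = 0, 3.6% (independent) to 9% (linear drift) at 0.01, and 15% to 34% at 0.05. It is too low, then too high, because the standard error itself is wrong.

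**5. Does the repair hold 5%?** A t test on club mean change or slope, on 2(k-1) df, gave 5.0% in every balanced setting. With unequal clubs and 40% retention (dropout at random, pattern assumed) it gave 4.8%-5.3%. The right variance with a z reference is not enough: P(|t| > 1.96) is 9.8% on 6 df and 18.9% on 2 df.

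**The case against.** **The text does not say intercepts only.** Calling club a random effect is compatible with a random slope, and so is the word trajectories. That stands: the fault depends on a reading. It is still the plain reading, because the sentence lists its random effects and no slope is among them.

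**The rate need not exceed 5% whenever clubs differ at all.** A reader might infer that any difference in club change breaks the test. The documents do not support this, because they state no degrees of freedom. Under residual or large-sample df the rate passes 5% for any club variance in change. Under club-based df on the same statistic it does so only above a threshold (step 4).

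**The size is assumed.** A reader might also infer serious inflation from the plan's ICC of 0.3. That figure concerns levels and cannot be converted into an ICC of change without a further assumption. Assessment 4 falls at about day 56, so differences in change may be small. The linear-drift figures are near the worst case for a linear-time test at a given ICC.

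**Covariate-constrained allocation could help.** The plan says "We will use a covariate-constrained approach". If the balanced covariates explain club differences in change, some inflation would be offset. This was not simulated.

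**A club-mean t test gives up the mixed model's use of incomplete records.** With "Considering 40% retention and 50 potential non-eligible, we will recruit 800 participants", that is a fair point. Informative dropout was not simulated, so there is no basis for ranking the t test above a club random slope.

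**Conclusion.** The omission is real and must be fixed before analysis. As read, the plan tests a club-randomised comparison of change against within-person error. The direction is certain under residual or large-sample df: above 5% if clubs differ in change, 5% if they do not. The size is unknown, because it depends on an ICC of change that the documents do not give. At an illustrative 0.01 the linear-time rate is about 9%-18% with 8 clubs of 37 and 14%-28% with 4 clubs of 75, and lower if only at-risk adolescents are analysed.

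These figures assume normal outcomes and balanced complete data. The H2 model lists the same random effects and should be checked for the same omission; no H2 error rate was computed.

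**What to change.** In Quantitative data analysis for Study 2:

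1. State the time coding and name one primary change contrast for both H1 models, for example a linear slope or baseline to one named assessment.
2. Test that contrast against between-club variation in the same contrast on 2(k-1) df, k being clubs per arm: 6 df with 8 clubs, 2 df with 4. Two routes are acceptable:
   - (a) keep the mixed model and add a club random slope, or a club × time effect matching the contrast, with Kenward-Roger df. State what is done if its variance is estimated as zero: dropping the term gives 3%-5% (8 clubs of 37) or 3%-7% (4 clubs of 75), while keeping 2(k-1) df is conservative;
   - (b) compare club mean changes or slopes between arms with a t test.
3. Do not pair the added variance term with a large-sample z reference.
4. Check the H2 model for the same omission.

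**Cost.** Wording only, no new data. If clubs do not differ in change, the 95% interval widens by 2.447/1.96 = 1.25 with 8 clubs and 4.303/1.96 = 2.2 with 4. Power was checked on the plan's own differences, treating them as baseline to Assessment 4 differences in change (hence equal baselines), with within-person residual 30%-70% of variance (assumed). With 8 clubs of 12 at-risk adolescents it stays at 96% or more for both outcomes up to an ICC of change of 0.05. With 4 clubs of 25 at 0.05 it is 64%-99% for intention and 48%-94% for positive social influence. The repair is affordable with 8 clubs and weakest at the 4-club minimum.
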